## Purpose of this SAP

The purpose of this Statistical Analysis Plan (SAP) is to provide a detailed and comprehensive plan for the statistical analyses that will be conducted on the data collected during the ESCAS study. The SAP ensures the transparency, consistency, and reproducibility of the study's data analysis, and helps avoid potential biases and data-driven decisions by prespecifying all planned analyses before data collection. This document will outline the statistical methods for analyzing the primary and secondary endpoints, as well as any exploratory endpoints, and will describe the approach for handling missing data, data transformations, and subgroup analyses.

By following this SAP, the study team can ensure that the results of the ESCAS study are analyzed and reported in a scientifically sound and rigorous manner, in accordance with best practices and regulatory guidelines. This will ultimately contribute to the assessment of the safety and efficacy of Cerebrolysin in the treatment of aphasia after acute ischemic stroke, and inform clinical decision-making and future research in this area.

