## Randomisation

Randomisation was discussed at length in the CSP. Briefly, patients meeting inclusion and exclusion criteria will obtain a random number corresponding to the random list generated in advance by a biometrician selected by the Coordinator. Three opaque randomization envelopes will be distributed: to the nurse in charge of preparing the infusion solution, to the study center in case of suspicion of harm to the patient, as well as to the study coordinator.

The study and database will be unblinded after closure of the database and determination of the analysis populations.

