### Data eligibility

Before unblinding, the statistician, having access to this SAP, will inspect the unblinded data to ensure correct format. Any abnormalities will be discussed and solved preferably before unblinding. After unblinding, a second round of data inspection will be performed, and if required, corrections to the SAP will be issued.

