## Analysis of subgroups

Subgroup analysis will be planned and executed after unblinding, if their distribution of demographic groups across trial arms allows for it.

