## Source code

Supplementary file 1 is provided at the end of this SAP, representing the source code for statistical analysis using R. Ideally, this code should not be changed after unblinding. Still, due to discrepancies between databases before and after unblinding, minimal adjustments to the statistical routines (especially for data loading) might be required. All subsequent source code changes should be documented, and the final source code version used in statistical analysis should be made available together with the CSR.

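### The SAP promises full prespecification, yet allows unlimited, unlabelled SAP corrections after unblinding and leaves all subgroup planning until then

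*SAP*

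**What the plan says.** - **Purpose of this SAP.** The document "helps avoid potential biases and data-driven decisions by prespecifying all planned analyses before data collection". The same section says that it "will describe the approach for handling missing data, data transformations, and subgroup analyses".
- **Randomisation.** "The study and database will be unblinded after closure of the database and determination of the analysis populations".
- **Data eligibility**, on the first inspection: "Before unblinding, the statistician, having access to this SAP, will inspect the unblinded data to ensure correct format". On problems found: "Any abnormalities will be discussed and solved preferably before unblinding". On what follows: "After unblinding, a second round of data inspection will be performed, and if required, corrections to the SAP will be issued".
- **Analysis of subgroups**, in full: "Subgroup analysis will be planned and executed after unblinding, if their distribution of demographic groups across trial arms allows for it".
- **Source code.** "Ideally, this code should not be changed after unblinding". The section then expects only minimal adjustments, mainly to data loading. It requires code changes to be documented and the final code to be supplied with the study report.

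**The concern.** A SAP protects against data-driven choices only if it is closed before anyone knows the allocation, or if later choices are visibly marked as later. Here one rule lets the SAP be corrected with the arms known, and another starts subgroup planning at that point. Neither says that the outcome must be reported as post hoc. Someone who followed both rules exactly could report a changed analysis, or a subgroup picked with outcomes by arm in view, as part of the plan. The false-positive rate of such results would be unknown, and the reader of the report could not tell them from the analyses fixed in advance.

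The sentence about inspecting unblinded data before unblinding is a separate wording fault in the same section. Applied literally, it would break the blind.

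**Working it through.** The SAP states no figure on this point that could be reproduced. The check is mainly a comparison of sections.

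**1. Changes to the SAP.** The Purpose section promises prespecification of all planned analyses. Data eligibility allows corrections after a second, post-unblinding inspection. The only condition is that they be required, and the clause does not say who decides this, what may be corrected or how the result is labelled. Source code shows the kind of limit that is missing: minimal, mainly for loading, documented. No equivalent exists for the SAP, which governs the code. Data eligibility also makes resolving abnormalities before unblinding a preference, not a requirement.

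**2. Subgroups.** The Purpose section promises a described approach. Analysis of subgroups gives only a time (after unblinding) and a condition (the spread of demographic groups across arms). It gives no variable, number, cut-point or test. The planned tables and graphs contain no subgroup output, and the R code has no subgroup routine, so nothing elsewhere in the SAP fills the gap.

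**3. Inspecting unblinded data.** The sentence opens by placing itself before unblinding, so its object contradicts its own first words. It also conflicts with Randomisation, which puts unblinding after database closure and after the populations are determined. The stated purpose is a format check. The R code loads a file that its comments call a test database for the allocation, and the comments expect that part to be adapted after unblinding. The likely intended word is *blinded*.

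**4. Size, as an illustration only.** The SAP gives no number of subgroups, so the count k is an assumption.
- Inputs: alpha = 0.05 (Statistical analysis). Comparability between study groups lists six baseline variables that are not scale scores: age, gender, education level, writing hand, alcohol abuse and other substance abuse.
- Assumed range: one test per variable, k = 6, or two levels per variable with a between-arm test in each, k = 6 × 2 = 12. One endpoint at one visit.
- Formula, independent tests and no true effect: P(one or more false positives) = 1 − (1 − 0.05)^k.
- k = 6: 1 − 0.95^6 = 1 − 0.735 = 0.265, about 26%.
- k = 12: 1 − 0.95^12 = 1 − 0.540 = 0.460, about 46%.
- Smaller counts: k = 3 gives 0.143 and k = 5 gives 0.226.

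For a given k these are ceilings. Subgroups on different variables reuse the same patients, so the tests are correlated, and correlation lowers the chance that at least one two-sided test is falsely positive. Two levels per variable is also a simplification: the R code has five education levels and three each for alcohol and other substances.

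**The case against.** The strongest reply is that the core of the plan is fixed. Statistical analysis and Exploratory statistics set out a rule for choosing each test, and the full R code is attached. Source code discourages changes after unblinding and requires them to be documented. Randomisation has the populations settled before unblinding. Confirmatory statistics says that no confirmatory analysis is planned, so no formally controlled error rate is at risk. The SAP also says openly that subgroups come later, and its stated condition is demographic balance, not outcome. SAP corrections follow a data inspection, and no section invites a new choice of endpoint or test.

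Most of this stands and limits the point. It does not remove the contradiction. An exploratory label does not turn a choice made after unblinding into a prespecified one, and the protection given to the code does not extend to the SAP text or to the subgroups.

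Three stronger readings are tempting, and the document does not support them:
- *The statistician is given early access to treatment allocation.* The sentence contradicts itself, Randomisation says otherwise, and the code was set up on a test allocation file. This is a wording error to correct, not evidence of early unblinding.
- *Per-protocol membership is decided with the arms known, because the code reads the per-protocol flag and the treatment flag from one file.* That is the test file, and its loading code is marked as provisional. Storing two columns together does not show when either was decided, and Randomisation states that the populations are determined first.
- *The whole plan loses its prespecified status.* The written tests and code for the main comparisons are unaffected unless they are changed after unblinding.

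**Conclusion.** The point holds in a limited form. The SAP contradicts its own promise in two places: SAP corrections after unblinding have no limit on scope and no post hoc label, and subgroups are planned only after unblinding with no content given now. A third place, the inspection of unblinded data before unblinding, is a self-contradiction and probably a slip.

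What is at risk is the interpretation of subgroup results and of anything altered after unblinding, not the main comparisons as written. The 26% to 46% range rests on an assumed 6 to 12 independent tests at 0.05 and is a ceiling for those counts. It says nothing about the effect of SAP corrections, which cannot be quantified from the document. The change should be made because it costs very little and removes rules that permit data-driven choices.

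**What to change.** - **Data eligibility, first inspection.** Replace *unblinded data* with *blinded data (dummy allocation codes)*.
- **Data eligibility, last sentence.** Replace it with a rule that the SAP and code are locked before unblinding, and that any later change is documented as a deviation and its results are labelled post hoc. Reconcile Source code with this rule. A pure data-loading adjustment, which that section already foresees, changes no analysis and needs only to be documented.
- **Analysis of subgroups.** Choose one of two routes. Either name, before unblinding, a short list from baseline variables already collected (for example baseline WAB Aphasia Quotient, NIHSS and age), with cut-points and an arm-by-subgroup interaction test. Or state that all subgroup analyses are post hoc and hypothesis-generating.

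**Cost.** The first two changes, and the second route for subgroups, are wording only. The first route also needs an interaction model and code for it, because the plan now has only two-sample, paired and contingency-table tests. The remaining cost is less freedom after unblinding; later analyses stay possible but must be labelled.

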### Missing data handling

In our study, missing data is considered missing completely at random (MCAR).

Statistical procedures were chosen such that missing data points have minimal effect over data usability. As such, we avoid data imputation, choosing between two methods of record deletion: listwise and pairwise.

Listwise deletion means the analysis of only patients that have complete data for all variables; if any data point from any variable is missing, the patient is excluded from all analyses. This means that, for example, data from a patient missing one WAB value will not be taken into consideration during the analysis of mRS values. Listwise deletion has the advantage of being straightforward and easy to understand, at the cost of a reduced sample size. In our study, listwise deletion is used in analysis of the PP population.

Pairwise deletion means the analysis of all patients that have the required data points for individual statistical tests, irrespective of missing values from variables not included in the tests. This means that, for example, data from a patient missing one WAB value will be taken into consideration during the analysis of mRS values, but the same patient will not be included in analyses involving that specific missing value. Pairwise deletion has the advantage of retaining more data into the statistical analysis, with the cost of increased complexity (each statistical test having different sample sizes) and the assumption of independence of missing at random values. In our study, pairwise deletion is used in analysis of ITT population.

## Statistical methodology

### Data handling

Part of the data handling procedure was previously described in the Coding systems utilized. Briefly, the database containing the raw patient information from the CRFs will be converted to a long format database with visit number and patient randomization number to identify each measurement/score for each scale. This specific format is chosen in order to better facilitate the comparisons, as well as graphics generation with ggplot2.

### Descriptive statistics

The following demographic data will be presented as part of the descriptive statistics: age at stroke onset, gender, educational level, writing hand, alcohol and other substance abuse, as well as baseline WAB and NIHSS scores. Quantitative variables will be described as mean±standard deviation, while qualitative variables will be described through absolute and relative frequencies.

Average scores for each scale at each time point and for each group will be presented in table format, as well as in boxplot graphics.

### Confirmatory statistics

No confirmatory analysis planned.

## Comparability between study groups

Compatibility between groups will be tested for the following variables: age (at stroke onset), gender, education level, writing hand, alcohol and other substance abuse, WAB scores (and their specific subscales) and NIHSS scores.

- Dichotomous variables will be tested using Chi test or, where its assumptions are not met due to small group size, Fisher's exact test.
- Qualitative ordinal variables, such as education level or alcohol/substance abuse, will be tested using Wilcoxon rank-sum tests.
- For quantitative variables, initially, normality distribution will be assessed for each group individually using the Shapiro-Wilk test. If the values for at least one group are not normally distributed, Wilcoxon rank-sum tests will be used. If values from both groups are normally distributed, equality of variances will be assessed using Bartlett test and then a Student T test for unpaired samples and equal or unequal variances will be used.

## Exploratory statistics

For WAB scores (and their specific subscales) as well as for NIHSS scores, we will calculate the differences between the scores at visits 2/3/4, and their corresponding baseline scores. These differences will be denoted with a lowercase letter "d." Throughout this section, we will refer to these values as *differentials*.

We will assess the normality of the differentials distributions for each group and visit using the Shapiro-Wilk test.

- If the distributions of the differentials show no statistically significant differences compared to the normal distribution, across all groups and visits, then those differentials will be tested against null hypotheses of  $\mu=0$  using one sample Student T test. This would be the equivalent of testing the values of the scores for each group, at visit 2/3/4, against the baseline measurements of each respective group using paired-sample Student T test. Moreover, for each visit, we will compare the differentials between groups using Student T test for unpaired samples and equal or unequal variances, depending on the result of a Bartlett test for variance equality between groups.
- In cases where significant differences exist in the distribution of the differential values for certain groups and visits, compared to the normal distribution, we will test all differentials against the null hypothesis of location=0 using a one-sample Wilcoxon signed-rank test. This approach is equivalent to comparing the values of the scores for each group at visits 2, 3, and 4 against their corresponding baseline measurements using a Wilcoxon signed-rank test. Moreover, for each visit, we will compare the differentials between groups using a Wilcoxon rank-sum test.

For BI and mRS scores, differences from visit 2 to visit 3 and 4 respectively will be assessed in the same way, with paired-sample tests, and differences between groups will be assessed using unpaired-samples tests. .

The number of patients with at least an active AE, SAE and specific AE class, will be reported. Incidence of AEs, SAEs and AE specific classes will be compared between groups using

Chi test or where its assumptions are violated, Fisher's exact test. Moreover, the number of AEs and SAEs for each patient will be compared between groups using Wilcoxon rank-sum tests.

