## Assumed parameters and resulted sample size

Using G\*Power 3.1.9.7 and assuming a medium effect size  $d=0.5$ , an alpha error of  $\alpha=0.05$  and  $\beta=0.2$ , with an allocation ratio of 1 for Wilcoxon-Mann-Whitney test between two groups, we obtained a sample size of 53 patients per group. In order to provide a margin of error for situations such as patient withdrawal, SAEs or protocol violations, we have decided to recruit 120 patients in total for our study, 60 for each arm.

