## Statistical analysis

For comparing numeric values of paired samples, differential values for each pair of values will be computed. Then, the distribution of those differentials will be compared with the normal distribution, using the Shapiro-Wilk test. If the differentials are normally distributed, we will use a one-sample Student T test (equivalent with the Student T test for paired samples) with null hypothesis  $\mu=0$ . If the differentials are not normally distributed, we will use a Wilcoxon signed-rank test with null hypothesis location=0.

For comparing numeric values of unpaired samples the normality of the values in each sample will be tested using Shapiro-Wilk test. If values from both samples are normally distributed, then variance equality between the samples will be assessed using the Bartlett test.

If the variances are equal, then the differences between the two samples will be assessed using a Student T test for unpaired samples and equal variances. If the variances are not equal, then a Student T test for unpaired samples and unequal variances will be used. In both cases, the null hypothesis will be that mean difference is equal to 0. If values from at least one of the samples are not normally distributed, then a Wilcoxon rank sum with null hypothesis of location difference equal to 0 will be performed.

For comparing ordinal values of paired samples, a Wilcoxon signed-rank test will be used, and for unpaired samples, a Wilcoxon rank-sum test will be used.

For comparing the difference in prevalences of variants of one dichotomous or nominal variable, among the groups of another dichotomous or nominal variable (i.e. testing the association between two dichotomous/nominal variables), the Chi test will be used or, where its assumptions would be violated (mainly due to small number of patients in any group), Fisher exact test will be used.

Where applicable, the two-tail p-value is reported. The type 1 error is assumed to be  $\alpha=0.05$ , and as such, results were considered statistically significant for  $p<0.05$ .

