# Some general functions ----
beautiful.p.value<-function(x){ #beautiful p value, if strictly under 0.001 print as <0.001,
otherwise print as =0.***
  x<-as.numeric(x)
  if(is.na(x))
    return("NA")
```

```
if(is.nan(x))
  return("NaN")
if(x<0.001)
  return("<0.001")
return(paste("",round(x,3),sep=""))
}
test.numeric.unpaired<-function(t1,t2){
  ret<-list()
  ret$sum_nas<-sum(is.na(t1))+sum(is.na(t2))
  t1<-t1[!is.na(t1)]
  t2<-t2[!is.na(t2)]
  if(length(unique(t1))==1)
    ret$shapiro.p.t1<-1
  else
    ret$shapiro.p.t1<-shapiro.test(t1)$p.value
  if(length(unique(t2))==1)
    ret$shapiro.p.t2<-1
  else
    ret$shapiro.p.t2<-shapiro.test(t2)$p.value
  if(ret$shapiro.p.t1<0.05|ret$shapiro.p.t2<0.05){ # if any of them is not normally distributed
    ret$final.test<-"Wilcoxon rank sum"
    ret$p.value<-wilcox.test(t1,t2,paired = F)$p.value
  }else{
    ret$bartlett.p<-bartlett.test(list(t1,t2))$p.value
    if(ret$bartlett.p<0.05){ # unequal distrib
      ret$final.test<-"Student T test for unpaired samples and unequal variances"
      ret$p.value<-t.test(t1,t2,paired = F,var.equal = F)$p.value
    }else{
      ret$final.test<-"Student T test for unpaired samples and equal variances"
      ret$p.value<-t.test(t1,t2,paired = F,var.equal = T)$p.value
    }
  }
  return(ret)
}
test.numeric.paired.2<-function(t1,t2){
  ret<-list()
  if(length(t1)!=length(t2))
    stop("Different lengths!")
  ret$na_vals<-is.na(t1)|is.na(t2)
  t1<-t1[!ret$na_vals]
  t2<-t2[!ret$na_vals]
  ret$shapiro.p.t1<-shapiro.test(t1)$p.value
  ret$shapiro.p.t2<-shapiro.test(t2)$p.value
  if(ret$shapiro.p.t1<0.05|ret$shapiro.p.t2<0.05){ # if any of them is not normally distributed
```

```

ret$final.test<-"Wilcoxon signed rank"
ret$p.value<-wilcox.test(t1,t2,paired = T)$p.value
}else{
ret$final.test<-"Student T test for paired samples"
ret$p.value<-t.test(t1,t2,paired = T)$p.value
}
return(ret)
}
test.numeric.paired.1<-function(tx){ #the same idea, but for when I supply only one group of
values
ret<-list()
ret$na_vals<-is.na(tx)
tx<-tx[!ret$na_vals]
ret$shapiro.p<-shapiro.test(tx)$p.value
if(ret$shapiro.p<0.05){
ret$final.test<-"Wilcoxon signed rank"
ret$p.value<-wilcox.test(tx)$p.value
}else{
ret$final.test<-"Student T test for one sample"
ret$p.value<-t.test(tx)$p.value
}
return(ret)
}
contingency.table.test<-function(t){
if(nrow(t)==2 & ncol(t)==2){
f<-fisher.test(t)
bigtotal<-sum(t)
can_use_chisq<-
(sum(t[1,])*sum(t[,1])/bigtotal>=5) &
(sum(t[1,])*sum(t[,2])/bigtotal>=5) &

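### The SAP text and its R code give two incompatible data-driven rules for choosing t test or Wilcoxon on the WAB AQ and NIHSS change scores

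*SAP*

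**What the plan says.** **Exploratory statistics.** Changes from baseline at visits 2, 3 and 4 are tested for normality in each arm at each visit. T tests apply if no significant departure is found "across all groups and visits, then those differentials will be tested against null hypotheses" of zero mean. Otherwise "we will test all differentials against the null hypothesis of location=0 using a one-sample Wilcoxon signed-rank test", and the arms are compared by rank-sum at every visit.

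**Statistical analysis (general rules).** Only the samples in the comparison at hand are examined: "If values from at least one of the samples are not normally distributed, then a Wilcoxon rank sum" test is used; otherwise Bartlett's test selects the form of t test. Paired comparisons are likewise decided one at a time, on their own differences.

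**R source code.** `test.numeric.unpaired` branches on "if(ret$shapiro.p.t1<0.05|ret$shapiro.p.t2<0.05){ # if any of them is not normally distributed". `table_them_all` calls it inside its loop over visits. In the same loop it calls `test.numeric.paired.1`, which has its own Shapiro-Wilk gate, once for each arm.

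**mRS.** The general section states: "For comparing ordinal values of paired samples, a Wilcoxon signed-rank test will be used", with rank-sum for unpaired samples and no normality test. The later section states: "For BI and mRS scores, differences from visit 2 to visit 3 and 4 respectively will be assessed in the same way" as WAB and NIHSS. The code puts mRS through the Shapiro-Wilk gate.

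**Context.** The sample size was computed "with an allocation ratio of 1 for Wilcoxon-Mann-Whitney test between two groups". On sidedness: "Where applicable, the two-tail p-value is reported". Confirmatory statistics says that no confirmatory analysis is planned, but p<0.05 is still the criterion for significance. Data eligibility allows SAP corrections after unblinding.

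**The concern.** A SAP should lead any two analysts to the same test. Here one who follows the endpoint section and one who runs the supplied code could apply different tests to the same WAB AQ data and report different p-values.

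The two tests also address different hypotheses: a difference in means for the t test, a shift in location for Wilcoxon. Under the code, Day 30 might be a statement about means and Day 90 one about location, and the two arms' within-group tests at one visit might differ in kind. Under the endpoint section the test is the same at every visit, but the data still choose it. Because the SAP may be corrected after unblinding, the conflict could end up being settled with treatment assignments known.

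**Working it through.** **1. The plan's own figure.** Inputs from the sample size section: d = 0.5, alpha 0.05, power 0.80, 1:1, Wilcoxon-Mann-Whitney. Method: noncentral t power with n multiplied by the asymptotic relative efficiency, 3/π = 0.955, for a normal parent.
- One-sided: 53 per group, power 80.3%. The stated 53 is reproduced.
- Two-sided: 67 per group. At 60 per arm, two-sided power is 75.6%.

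The test family is therefore Wilcoxon, and 53 corresponds to a one-sided test. The sidedness is a separate issue.

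**2. How many rules there are.**

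| Score | Statistical analysis | Exploratory statistics | R code |
|---|---|---|---|
| WAB AQ, NIHSS change | per comparison | one choice for all visits | per comparison |
| mRS | always Wilcoxon | same approach as WAB and NIHSS | per comparison, Shapiro-Wilk gate |

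For WAB AQ and NIHSS there are two rules. The general section and the code agree, and the endpoint section differs.

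**3. Arithmetic for exactly normal data.** Assume independent Shapiro-Wilk tests at 0.05, two arms and three visits, with the endpoint rule applied to each score separately.
- Wilcoxon at a given visit under the code: 1 − 0.95² = 9.8%.
- Wilcoxon throughout under the endpoint section: 1 − 0.95⁶ = 26.5%.
- Different Day 90 tests: no rejection at Day 90 but at least one at an earlier visit, 0.9025 × (1 − 0.9025²) = 16.7%.
- Tests mixed across visits under the code: 1 − 0.0975³ − 0.9025³ = 26.4%. Under the endpoint section this cannot happen.

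Disagreement runs one way only: the endpoint section gives Wilcoxon and the code a t test.

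**4. Simulation.** 60 per arm, three visits, Shapiro-Wilk and Bartlett at 0.05. The documents give neither the skewness of the change scores nor their between-visit correlation. The correlation was set to 0.7 and the skewness varied; for a gamma shape k it is 2/√k.

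| Distribution (skewness) | Different Day 90 test | Code mixes tests across visits |
|---|---|---|
| Normal (0) | about 15% | about 25% |
| Gamma, shape 20 (0.45) | about 33% | about 61% |
| Gamma, shape 6 (0.82) | about 15% | about 36% |
| Gamma, shape 3 (1.15) | about 1% | about 4% |

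Disagreement peaks at mild skewness. With strong skewness nearly every Shapiro-Wilk test rejects and both rules give Wilcoxon.

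**5. Consequences.** As a share of all simulated trials, the Day 90 verdict at p<0.05 differed in 0% to 1.8%. In a separate run with a shift of 0 or 0.5 SD and skewness 0 to 1.2, the verdict differed at one or more of the three visits in 0.1% to 4%. Day 90 type I error lay between 0.035 and 0.061 over the runs under either rule; simulation error is about 0.006 at 1,500 trials per scenario.

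**6. mRS.** In simulated seven-level scores with 60 per arm, the code sent the between-group comparison to Wilcoxon in 99.5% to 100% of trials and the one-arm paired test in 90% to 100%. The t-test branch is seldom reached.

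**The case against.** The other side has good points.

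- *The specific section governs.* Exploratory statistics could be read as overriding the general section. The SAP states no such precedence, however, and this reading leaves the conflict with the code in place, because the code follows the general rule.
- *The code settles the matter.* It was supplied in advance and the Source code section wants it unchanged after unblinding, with any adjustments minimal and documented. A reader might infer that the choice of rule is wide open after unblinding; that is too strong. Data eligibility does, however, permit SAP corrections at that stage, and the text contradicts the code.
- *Pre-testing does no visible harm.* This stands. A reader might infer that the Shapiro-Wilk and Bartlett gates inflate the false-positive rate, but the simulated type I error does not show it.
- *The trial is exploratory.* True, and it lowers the weight. It does not justify two rules for one analysis when significance is still declared at p<0.05.
- *The mRS conflict is nominal.* It is real on the text but has little practical effect.

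**Conclusion.** The conflict holds for the WAB AQ and NIHSS change scores: two incompatible rules, no precedence, and code that does not carry out the endpoint section. The test, and with it the hypothesis, is not fixed, and under the code it can change between Days 30, 60 and 90.

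Two stronger readings are not supported. A reader might count three rules for the primary outcome, but the general section and the code agree. A reader might also conclude that two analysts would report different p-values; they could, but for normal data both rules pick the same Day 90 test in about 85% of trials.

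The effect on conclusions is small: at most about 2% of trials change their Day 90 verdict. That rests on 60 per arm, a correlation of 0.7 and the skewness values shown, all but the first assumed. The point should be corrected before unblinding for reproducibility, not because the error rate is at risk.

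**What to change.** Before unblinding:

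1. Name the two-sided Wilcoxon rank-sum test for the between-group comparison of WAB AQ and NIHSS differentials at all three visits, and the signed-rank test within arms. This is the test family on which the trial was sized.
2. Use Wilcoxon for mRS without any normality test. `table_them_all` also produces the Barthel Index table, so state that BI follows the same rule.
3. Remove the Shapiro-Wilk and Bartlett steps from the efficacy text in Statistical analysis and Exploratory statistics, and from the efficacy calls in `table_them_all`.
4. Do not simply delete the gate inside `test.numeric.unpaired`. The baseline table uses the same function, and Comparability between study groups prescribes the gate there for quantitative variables. Leave it unless that section is amended too.

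The cost is a few sentences and a shorter function. Statistically, the loss is 1 − 3/π = 4.5% efficiency if the data are exactly normal. In the simulations with a 0.5 SD shift, Day 90 power for rank-sum against t test was 75.7% against 77.3% for normal data, and 86.0% against 77.7% at skewness 1.2. The two-sided power of about 76% at 60 per arm and d = 0.5 should be known when the test is fixed, but it comes from the one-sided sample size and is a separate matter.
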